Immediate repercussions on the spine posture
from passive elevation of the heels in healthy subjects:
a cross-sectional study

12-10-2022

ID: H&S01

Approved by IRB ManusSapiens on 03-31-2022

Protocol n° 2022/001

(translated version)

Introduction / background

Women who wear high-heeled shoes are considered more attractive, self-confident and elegant.

Although commonly used in the female population, high-heeled shoes affect posture and gait and are generally thought to be associated with back pain (Lee et al 2001; Bird et al. 2003; Russell 2010). The most popular etiopathogenetic hypothesis linked to this association is a compensation strategy with an increase in lumbar lordosis (Russell 2010). Investigations into the role of high-heeled shoes in altering the spinopelvic profile attempted to explore compensatory and adaptive structural changes as a cause of lower back pain. The conclusions of these studies, however, are controversial. Some studies (Snow et al. 1994; Cowley et al. 2009; de Oliveira Pezzan et al 2011; Dai et al 2015), in fact, have shown that high-heeled shoes significantly increase lumbar lordosis (LL), and consequently mechanical loading and degenerative changes in soft tissues (Snow et al. 1994). Other studies (de Lateur et al 1991, Franklin et al 1995), on the other hand, showed a reduction in LL and a compensatory increase in the activity of the erector spinal muscle (Pezzan de Oliveira et al 2011). The results of other studies also indicated that heel elevation did not significantly change the LL in the subjects evaluated (Lee et al. 2001; Schroeder and Hollander 2018).

The results of Oliveira Pezzan et al. (2011) are indicative of an increase in pelvic anteversion and LL, but only in the group of subjects who frequently wore high heels, while the effect in the other group was a decrease in pelvic tilt and lordosis.

A precise, radiation-free and inexpensive method of detecting spinal posture, particularly for follow-up, is rasterstereography (Asamoah et al 2000; Drerup et al. 2001; Hierholzer et al. 2002). The surface analysis is carried out by projecting a light grid modeled on the patient's back. Anatomical landmarks can be automatically detected by assigning concave and convex areas. Through the detection of predetermined anatomical points, the system is able to calculate a three-dimensional model of the human spine.

From this model, relevant clinical parameters can be determined, such as: pelvic obliquity, trunk inclination and kyphosis and lordosis angles (Huysmans et al. 2005; Schulte et al 2008; Betsch et al. 2010).

The reliability coefficients of the rasterstereographic assessment method for the study of the sagittal plane were reported as excellent ($ICC > 0.95$) for both intra-examiner (Schroeder et al. 2015) and inter-examiner (Mohokum et al. 2010). Another systematic review (Mohokum et al. 2015) concluded that rasterstereography can be considered valid for both screening and monitoring.

A recent study (Schroeder and Hollander 2018) used rasterstereography (spinometry) to evaluate the immediate effect in a group of young (less than 24 years old) and middle aged (24 to 56 years old) women who are habitual wearers of high-heeled shoes, after wearing their shoes without heels and with an average heel of 8.7 cm. The results are indicative of a reduction in pelvic tilt and not of lordosis when using the shoe with the heel.

Objective of the study

The aim of this study is, given the remarkable heterogeneity of the data in the literature, to investigate whether artificial heel lift affects spinal posture and pelvic position in the sagittal plane in a group of healthy men and women. A better understanding of the immediate reaction of the spinal column in search of equilibrium during heel lifting could increase the knowledge useful for understanding low back pain associated with the use of shoes with heels and help preventing and/or treating it.

What is meant to prove

The aim of this study is to investigate whether artificial heel lift immediately influences spinal posture and pelvic position in the sagittal plane in a group of healthy male and female subjects not used to wear high-heeled shoes. The recent study by Schroeder and Hollander (2018) used a sample of female subjects with habitual heels; moreover, compared to the previous work, this research also includes the investigation at the level of dorsal kyphosis.

What is added to current knowledge

Given the extreme variability of the data reported in the literature, a better understanding of the adjustments of the immediate reaction of the spine and pelvis to heel elevation. These data could increase knowledge of the pathogenesis of low back pain related to heel height and help prevent or treat it.

Primary outcome: investigate the immediate postural response of the pelvis, lumbar and dorsal spine in search of balance during the passive elevation of 3 cm and 7 cm of the heels with a non-invasive tool in non-users of high-heeled shoes.

Secondary outcome: investigate if there is a different response in the two sexes. Assuming that the reaction to heels can also be linked to the habit of wearing high-heeled shoes, use the response of a group of males, who are assumed to have never worn high-heeled shoes (7 cm) in their own life, can further clarify what type of response occurs in the search for immediate postural balance of the pelvis and the dorsal-lumbar spine after the raising of the heels.

Study design

Cross sectional study. Monocentric.

Duration of the study

Six months

Materials and methods

Setting: OSCE (Osteopathic Spine Center Education), osteopathic school based in Bologna.

Population: 100 students (50 females and 50 males) to be enrolled in OSCE school by making announcements during the lessons. The number of subjects to be evaluated was decided on the basis of the most recent work which used the same methodology, which evaluated a sample of 36 women (Schroeder and Hollander 2018). A similar number between males and females was set to improve the statistical comparison.

Following the ethical principles of the Declaration of Helsinki, a paper information will be provided where there will be an explanation of the intent and purpose of the study to all subjects prior to their participation; in addition, a paper consent will be provided, together with the information, on which to obtain the voluntary written informed consent.

Inclusion criteria: asymptomatic young subjects.

Exclusion criteria:

- structural or neurological anomalies that may prevent from maintaining an upright position for 5 sec. with their heels elevated on a 7 cm high basement;
- habitual users of shoes with 7 cm high heels, with a frequency of at least twice a week and / or less than 3 hours / week as proposed by a previous study (de Oliveira Pezzan et al. 2011);

- low back pain in the past 30 days.

Measurement method

A three-dimensional posterior surface analysis is performed with the Formetric 4D® rasterstereographic device (Diers International GmbH, Schlangenbad, Germany). The device, already supplied at the Spine Center rehabilitation center in Bologna and made available free of charge for the study, is non-invasive and non-dangerous. The analysis of the spine curve with rasterstereography is performed with a purely optical modality.

[figure not shown]

fig. 1 - Scheme of the spinometric parameters to be recorded: pelvic inclination, lordotic angle, kyphotic angle.

[figure not shown]

fig. 2 - Scheme of the spinometric parameters to be recorded: cervical and dorsal arrow, anterior flexion of the trunk.

Investigated parameters

The data collected by the Formetric evaluation will be:

- 1) pelvic tilt angle (PI), the angle determined by the vertical and the tangent to lumbosacral junction (ILS);
- 2) ITL-ILS lordotic angle, measured between the tangents of the thoracolumbar junction (ITL) and the lumbosacral junction (ILS);
- 3) ICT-ITL kyphotic angle, measured between the tangents of the cervicothoracic junction (ICT) and the thoracolumbar junction (ITL); see fig. 1;
- 4) lumbar arrow (FL) horizontal distance in millimeters from the vertical line that passes through the kyphotic apex in the lumbar spine;
- 5) cervical arrow (FC) (horizontal distance in millimeters from the virtual vertical plumb line that passes through the kyphotic apex in the cervical spine);
- 6) antero-posterior flexion of the trunk (Trunk Inclination-TI) measured as the angle between the vertical line and the line passing through the prominent cervical vertebra (VP) to the line connecting the two dimples (DM); see fig. 2.

Participants will provide information on age, height and weight. A questionnaire will be administered to standardize the types of high-heeled shoes used and to verify their frequency of use.

Evaluation Protocol

- 1) sample 1: barefoot neutral position;
- 2) sample 2: barefoot neutral position;
- 3) sample 3: 3 cm rise under both heels;
- 4) sample 4: 7 cm rise under both heels.

The positioning with respect to the measurement system will be carried out according to the indications provided by the supplier.

To standardize the position subjects will be prepared for analysis as follows:

1. standing, back to the detection system, in a relaxed posture with the knees fully extended with bare feet on the floor (neutral position);
2. bare trunk with pants and briefs lowered to half of the glutei
3. in the case of long hair, it will be required to tie it with suitable means (cap, hair clips, hair bands, etc.) so that the neck is visible up to the hairline;
4. rings, watches and necklaces will be removed to avoid any interference with light lines (necklaces in particular increase this probability).

In the third survey, the heel will be raised by inserting a plastic bar symmetrically under both heels, as proposed in previous studies in which wood was used (Bendix et 1984; Franklin et al. 1995), by 3 cm; for the fourth evaluation it will be 7 cm.

After the first evaluation in the neutral position, before the evaluation with the heel lift, a second evaluation will be performed under the same conditions to evaluate the reproducibility of the data. The time between the two assessments will be less than 1 minute and the subject will not change position.

The spinometric analysis will be performed by specialized operators; the data will be entered after anonymization with an identification code on an Excel spreadsheet; the statistical analysis will be performed with the Prisma statistical program.

Statistic analysis

Descriptive analysis will be performed to determine mean values and standard deviations (SD).

It will be used:

- Kolmogorov-Smirnov test to verify the normal distribution;
- intra-class correlation coefficient test (ICC) and the t-test for paired data to evaluate the repeatability of the data between the first and second detection in neutral conditions;
- One-way ANOVA and paired t-test for data for comparison between neutral position, heels raised by 3 cm and 7 cm in both males and females;
- Cohen's d will be calculated for the difference between neutral conditions (NEU) and those with the rise (3-7cm) (d = 0.20 indicates a small effect size, d = 0.50 an effect size mean and d = 0.80 a large effect).
- t-test for independent data to evaluate if there are significant differences between the different positions (0-3 cm-7cm) between males and females.

Statistical significance will be accepted for p values <0.05.

Data analysis will be performed using Prism 8 software (Graphpad Software, S. Diego).

Bibliography

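### The male-female comparison cannot separate sex from residual heel experience, because men's non-use is assumed, women need not be never-users, and the heel-use questionnaire enters no analysis

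*Combined protocol and SAP*

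**What the plan says.** The secondary outcome is stated as a sex question: "Secondary outcome: investigate if there is a different response in the two sexes". Its rationale is heel habit: "Assuming that the reaction to heels can also be linked to the habit of wearing high-heeled shoes", the response of men is expected to clarify the picture, since they are people "who are assumed to have never worn high-heeled shoes (7 cm) in their own life".

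The exclusion criteria (Materials and methods) remove "habitual users of shoes with 7 cm high heels, with a frequency of at least twice a week", followed by an and/or clause reading "less than 3 hours / week as proposed by a previous study". No criterion requires women never to have worn heels.

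Under Investigated parameters: "A questionnaire will be administered to standardize the types of high-heeled shoes used and to verify their frequency of use". The items are not shown.

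The Statistic analysis section plans one comparison between the sexes: "t-test for independent data to evaluate if there are significant differences between the different positions (0-3 cm-7cm) between males and females". It names no covariate, stratum, subgroup or table based on heel use.

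The Introduction reports one earlier study in which pelvic anteversion and lordosis increased, but "only in the group of subjects who frequently wore high heels"; the other group showed a decrease.

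**The concern.** Sex is being used partly as a stand-in for heel exposure. Men are taken to have none. Women may have some, because the exclusion stops at habitual 7 cm use, and the Introduction itself says that such shoes are common among women. The hours clause does not help: as worded it sets no upper limit on use, and it needs to be reconciled with the frequency clause and with the aim of studying people not used to high heels.

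Sex and heel experience are therefore likely to differ together. If experience alters the response, the unadjusted t-test attributes its effect to sex. It could equally hide a real sex difference that runs the other way. What is at stake is the interpretation of the secondary outcome, on the very point for which the protocol says men were included.

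**Working it through.** **No figure in the plan to reproduce.** The sample of 100 (50 per sex) is justified by an earlier study of 36 women. No power, effect size or SD is given.

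**Inputs from the documents.** 50 women, 50 men, significance at p < 0.05 (taken as two-sided).

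**Inputs assumed.** f = share of women with some heel experience; h = shift in response caused by that experience, in SDs of the change from neutral; true sex effect = 0. The documents give neither f nor h, so ranges are shown.

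**Step 1: bias.** The expected spurious difference is f × h. For f = 0.5 and h = 0.5 it is 0.25 SD.

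**Step 2: chance of p < 0.05 when change scores are compared.** The noncentrality is f·h / √(1/50 + 1/50) = f·h / 0.2. For f = h = 0.5 it is 0.25 / 0.2 = 1.25, which with 98 degrees of freedom gives 24%. Simulation (20,000 runs) gives 23%, slightly lower because mixing users and never-users widens the women's SD.

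**Step 3: the same if the t-test is run at each position.** The plan's wording can be read this way. Between-subject variation in posture then dilutes the shift. Assuming the position SD is twice the change SD, the standardised bias is f·h / 2.

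| f | h (SD of change) | bias f·h | spurious p < 0.05, change | spurious p < 0.05, each position |
|---|---|---|---|---|
| 0.3 | 0.3 | 0.09 | 7% | about 5% |
| 0.5 | 0.5 | 0.25 | 23% | about 9% |
| 0.5 | 0.8 | 0.40 | 48% | about 17% |
| 0.8 | 0.5 | 0.40 | 50% | about 17% |
| 0.8 | 0.8 | 0.64 | 87% | about 35% |

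For lighter assumptions, f = 0.25 with h = 0.2 or 0.5 gives 6% or 10% on change scores (noncentral t).

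**Step 4: masking.** A true sex effect of 0.5 SD opposed by a 0.5 SD experience shift in half the women leaves 0.5 − 0.25 = 0.25 SD. Power on change scores falls from 70% to 23%.

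**Step 5: what adjustment estimates.** Take change = a + b·(female) + c·(any use). If every man is a never-user there are three cells: men (a), never-user women (a + b) and user women (a + b + c). Three parameters fit three means exactly, so b is the difference between never-user women and men. Covariate adjustment and restriction to never-users therefore give the same point estimate, and asking for both adds no safeguard.

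**Step 6: cost in precision of a never-user comparison with 50 men.** Noncentrality at d = 0.5 is 0.5 / √(1/50 + 1/n); detectable d at 80% power is (1.96 + 0.84) × √(1/50 + 1/n).

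| never-user women (n) | power at d = 0.5 | detectable d, 80% power |
|---|---|---|
| 50 | 70% | 0.56 |
| 38 | 63% | 0.60 |
| 25 | 52% | 0.69 |
| 12 | 33% | 0.90 |
| 10 | about 30% | 0.97 |

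**The case against.** The strongest reply is that the evidence for a habit effect concerns people the study means to leave out. The reversal reported in the Introduction was seen in frequent wearers; the exclusion is aimed at habitual users and cites that same study. Nothing in the documents shows that occasional, past or lower-heel use changes the response. This stands: a reader might infer that habit is known to reverse the response in the women enrolled here, and the documents do not support that.

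Second, the stated question is whether the sexes differ; habit is a premise and not a quantity to be estimated. This also stands. A reader might infer that the secondary question cannot be answered at all, or that a real sex difference would be reported as a habit effect. Neither follows: the t-test can show whether the sexes differ, and no habit effect is analysed. What it cannot supply is the reason for a difference.

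Third, the upper figures depend on unsourced prevalence and shift and on change scores. That is correct, and for this reason 87% should not be quoted alone.

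Fourth, the questionnaire may serve only to check eligibility and may not record lifetime use. That is possible, so the needed variable cannot be assumed to be in hand. The questionnaire is not restricted to women either, so men may already be asked. None of this gives heel use a place in the analysis, and the exclusion does not make the sexes equal in exposure.

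**Conclusion.** The point holds as a limit on interpreting a secondary comparison. Men's non-use is assumed, women's lighter use is allowed, and the plan has no analysis that would show whether heel experience contributes to a male-female difference. The bias could be negligible, if few women have worn heels or light use matters little, or large. The 7% to 87% range for change scores, and about 5% to 35% for tests at each position, describe assumed scenarios and are not predictions; the second range also assumes a position SD twice the change SD. The primary comparison of 0, 3 and 7 cm is within subject and is not touched.

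**What to change.** 1. Give the questionnaire to both sexes, make sure it records never versus any heel use, and tabulate heel use by sex. Reconcile the frequency and hours clauses of the exclusion criterion.
2. Keep the planned sex comparison. Add one pre-specified sensitivity analysis: the change from neutral at 3 cm and at 7 cm in never-user men against never-user women, as an estimate with a 95% CI.
3. Report the response by heel use within women as descriptive only, so that it does not add further tests over six parameters and two heights.
4. Word the conclusion as a male-female difference that may reflect heel experience, unless the never-user estimate is of similar direction and size. Do not require that estimate to be significant.

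The cost is some added wording, possibly one questionnaire item, and a small extra analysis with no new subjects or measurements. The downside is the loss of precision shown above. If very few women turn out to be never-users, the table of heel use by sex will itself show that a conclusion about sex alone is not supported.

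### The exclusion rule for habitual heel users joins a minimum frequency to a maximum number of hours by an and/or, so no literal reading that uses the hours limit sorts users from non-users consistently

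*Combined protocol and SAP*

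**What the plan says.** The study is aimed at people who do not habitually wear heels. What is meant to prove describes them as "healthy male and female subjects not used to wear high-heeled shoes", and the Primary outcome sets the question "in non-users of high-heeled shoes".

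One line under Materials and methods, Exclusion criteria, turns this into an eligibility decision. It excludes "habitual users of shoes with 7 cm high heels", qualified as "with a frequency of at least twice a week and / or less than 3 hours / week", and refers to an earlier study for the definition. No other section defines habitual use, resolves the and/or or restates the hours limit.

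The Secondary outcome gives heel habit a role in the comparison of the sexes. It begins "Assuming that the reaction to heels can also be linked to the habit of wearing high-heeled shoes" and then brings in men "who are assumed to have never worn high-heeled shoes (7 cm) in their own life". Investigated parameters names the tool for ascertaining use: "A questionnaire will be administered to standardize the types of high-heeled shoes used and to verify their frequency of use". Hours per week are not mentioned there. The title page marks the text as a translation.

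**The concern.** A rule that excludes habitual users should become more likely to exclude a person as use goes up. Here the frequency limit is a lower bound, so it does that. The hours limit is an upper bound, so it does the reverse. The and/or leaves open how the two combine, and two people screening from this text could decide differently about the same student.

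What is at stake is the meaning of non-user. The men are assumed never to have worn 7 cm heels, so any users let in would be mainly women. If users react differently, some of the effect of habit would enter the estimate in women and the planned male-female comparison (Statistic analysis: "t-test for independent data to evaluate if there are significant differences between the different positions (0-3 cm-7cm) between males and females"). That harm is conditional, and the background is mixed on the condition. The Introduction reports opposite responses in frequent wearers and in others in one study. It also reports, from the most recent study, reduced pelvic tilt in habitual wearers, which is the direction the first study gave for its non-frequent group.

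**Working it through.** **Inputs.** Let f be times per week and h be hours per week. From the Exclusion criteria, the frequency limit is f ≥ 2, the hours limit is h < 3, and the connective is and/or. The men's assumed use is f = 0, h = 0 (Secondary outcome). The plan gives no figure to reproduce.

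**Test.** A reading fails if it excludes one person and admits another whose frequency and hours are both at least as high. This test needs no view on which cut-off was intended.

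| Pattern (f / h) | AND | OR, literal | OR, wearers only | Exactly one | Hours only | Frequency only |
|---|---|---|---|---|---|---|
| 0 / 0 | admit | exclude | admit | exclude | exclude | admit |
| 1 / 1 | admit | exclude | exclude | exclude | exclude | admit |
| 1 / 8 | admit | admit | admit | admit | admit | admit |
| 2 / 2 | exclude | exclude | exclude | admit | exclude | exclude |
| 2 / 6 | admit | exclude | exclude | exclude | admit | exclude |
| 5 / 40 | admit | exclude | exclude | exclude | admit | exclude |

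- AND fails: 2/2 is out and 5/40 is in.
- Literal OR fails: 0/0, the target group and all the assumed never-wearing men, is out and 1/8 is in.
- OR confined to wearers fails: 1/1 is out and 1/8 is in.
- Exactly one fails: 1/1 is out and 2/2 is in.
- Hours only fails: 0/0 is out and 5/40 is in.
- Frequency only passes, but the hours limit then does nothing.

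**Does turning the inequality round settle it?** With h ≥ 3 in place of h < 3 (the present numbers, as an example only), both connectives pass the test but give different rules. Same-direction AND excludes 2/6 and 5/40 and admits 1/8 and 2/2. Same-direction OR excludes all four. The connective therefore has to be stated as well.

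**Illustration of size.** Every input here is assumed except 50 women and 50 men (Population). Non-users change by a mean of 0.5 SD. A share p of the women are users with mean change u. The women's mean is (1−p)·0.5 + p·u, and their SD is √[1 + p(1−p)(0.5−u)²]. Power is for a two-sided 5% paired t-test with n = 50 (noncentral t, 49 df). The false sex-difference rate is for an independent t-test on change, with men at mean 0.5 and SD 1 (98 df).

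For p = 5% and u = −0.5, the mean is 0.95·0.5 − 0.05·0.5 = 0.45 and the SD is √(1 + 0.0475) = 1.0235. The noncentrality is 0.45/1.0235·√50 = 3.11, giving power of 86.2%. For the sexes, (0.5 − 0.45)/√[(1 + 1.0475)/50] = 0.247, giving a rate of 5.7%.

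| u | Power in women at p = 2 / 5 / 10 / 20% | False sex-difference rate at p = 2 / 5 / 10 / 20% |
|---|---|---|
| 0.5 (same as non-users) | 93.4% throughout | 5.0% throughout |
| 0.25 (half response) | 92.9 / 92.1 / 90.7 / 87.4% | 5.01 / 5.04 / 5.18 / 5.70% |
| 0 (no response) | 92.3 / 90.5 / 87.0 / 77.6% | 5.03 / 5.17 / 5.70 / 7.80% |
| −0.5 (opposite response) | 90.9 / 86.2 / 75.7 / 48.8% | 5.11 / 5.69 / 7.73 / 15.87% |

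The planned sex comparison can also be read as a test on raw values at each position. The raw SD is then 1/√[2(1−r)] change SDs, where r is the within-person correlation. For u = −0.5, with equal neutral means, the rates at p = 2 / 5 / 10 / 20% are 5.04 / 5.28 / 6.11 / 9.46% at r = 0.8 and 5.01 / 5.07 / 5.28 / 6.12% at r = 0.95 (both values of r assumed).

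**The case against.** The best reply is that the intent is clear enough. The phrase "habitual users of shoes with 7 cm high heels" and the stated non-user population make it unlikely that anyone admitted a 40-hour wearer or turned away the men. Twice a week or more is a workable cut-off by itself, and the questionnaire is described as checking frequency, which suggests that frequency was the operative test. The text is a translation. Those who screened may have worked from an original that reads correctly, and a lost negative would explain the reversed hours limit.

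Much of this stands. It limits the point to the text as written and makes a large practical effect unlikely. It does not recover the rule. A lost negative would mend the direction but not the and/or. Reading the hours limit as an exemption (twice a week or more, unless under 3 hours) also makes sense, but it replaces the connective with a different word, so it corrects the text and does not interpret it.

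A reader might infer more than the documents support:

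- **That once-weekly wearers at 3 hours or more are wrongly admitted.** Every reading tabulated above admits them, but this is an error only if a lower limit on hours was meant. Under frequency only they are correctly admitted.
- **That some particular share of the women are users.** No section gives a distribution of heel use, and the questionnaire itself is not in the documents, so it may already record hours.
- **That power near 49%, or a false sex-difference rate near 16%, is to be expected.** Those figures need 20% users who respond in the opposite direction. The opposite response in the Introduction concerns frequent wearers, whom a sensibly applied rule would exclude.
- **That the primary analysis should move to the corrected rule.** Redefining eligibility with data in hand brings its own risk of bias, and nothing in the documents calls for it.

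**Conclusion.** The criterion contradicts itself as written. This rests only on its wording and on the principle that a rule against habitual users should not exclude a lighter user while admitting a heavier one. It holds for AND, for OR with or without a restriction to wearers, for exactly one of the two, and for hours alone. The documents cannot decide between a redundant hours limit, a reversed inequality and a translation slip.

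How many people are affected cannot be computed. The practical effect is probably small, because the surrounding text points screeners away from the extreme readings. The power and error-rate figures are illustration only, and they show no change at all if users respond as non-users do. The line should still be corrected: it is the only operative definition of the study population, and correcting it is cheap.

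**What to change.** Reconcile the criterion with the original-language protocol, with the definition it cites and with the non-user population in What is meant to prove and the Primary outcome. Restate it as one rule with a single connective that never excludes a lighter user while admitting a heavier one. The sponsor confirms the cut-offs and whether the hours limit stays. Apply the rule to both sexes. If the hours limit stays, make sure the planned questionnaire records hours per week as well as frequency.

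No start date is given, and enrolment may be over. If it has taken place, report which rule was actually applied and how many participants the reconciled rule would re-classify. Repeat the analyses without them as a sensitivity analysis where the recorded data allow.

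The cost is one protocol line, possibly one questionnaire item, and perhaps a few re-classified participants. If hours were needed but not recorded, going back to participants would require a retained key to the identification codes. The Evaluation Protocol says data are anonymised on entry and does not mention such a key.

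### The male-female t-tests, read literally, compare values at each heel height, so for the two millimetre parameters body size can appear as a sex difference and the question of response is not tested.

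*Combined protocol and SAP*

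**What the plan says.** All of the relevant text is in the combined protocol and SAP.

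- **Secondary outcome.** The question is whether the two sexes respond differently to heel elevation. Men are included because they are assumed never to have worn 7 cm heels.
- **Investigated parameters.** Four of the six are angles. The other two are distances: FL is a "lumbar arrow (FL) horizontal distance in millimeters from the vertical line" through the kyphotic apex, and FC is a "horizontal distance in millimeters from the virtual vertical plumb line that passes through the kyphotic apex in the cervical spine". Neither is scaled to height or trunk length. The same section states "Participants will provide information on age, height and weight".
- **Evaluation Protocol.** The rise is the same for everyone: "sample 3: 3 cm rise under both heels" and "sample 4: 7 cm rise under both heels".
- **Statistic analysis.** The only method listed for comparing the sexes is a "t-test for independent data to evaluate if there are significant differences between the different positions (0-3 cm-7cm) between males and females". Body height enters neither this nor any other listed analysis, whether as covariate, ratio or matching factor.
- **Population.** 50 women and 50 men, a number based on an earlier study of 36 women. No effect size, SD or power is given.

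**The concern.** A length in millimetres grows with the body even when the shape of the spine is the same. If one sex is larger on average, FL and FC will differ between the sexes at 0, 3 and 7 cm alike, with no difference in posture and none in reaction to the heels. An unadjusted t-test at each position cannot separate this from a postural difference.

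The second problem follows from the same wording and reaches all six parameters. A male-female difference at 7 cm that is already present at neutral says nothing about response, and response is what the secondary outcome asks about. At stake is the wording of the secondary conclusion: a report could present a difference in size, or a constant offset between the sexes, as a different reaction to raised heels.

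**Working it through.** The plan gives no figure to reproduce here: no SD, mean height, expected arrow length or power. The size of the problem is therefore worked out under stated assumptions.

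**Inputs from the plan:** 50 per sex; significance at p < 0.05 (two-sided assumed, as sidedness is not stated); effect-size benchmarks of 0.20, 0.50 and 0.80.

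**Inputs assumed:** a relative size difference *s* between the sexes of 5% to 10%; a CV of FL or FC of 25% to 50%; a standardised response (mean change / SD of change) of 0.2 to 0.8, spanning the plan's own benchmarks.

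**Step 1: values at each position.** If shape is identical and the distance scales with size, the spurious standardised difference is d = s / CV. The rejection rate comes from the noncentral t with 98 degrees of freedom and noncentrality d × √(50/2) = 5d.

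| s | CV | d | 5d | Rejects |
|---|---|---|---|---|
| 5% | 50% | 0.10 | 0.5 | 7.9% |
| 5% | 25% | 0.20 | 1.0 | 16.8% |
| 10% | 50% | 0.20 | 1.0 | 16.8% |
| 10% | 25% | 0.40 | 2.0 | 50.8% |

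**Step 2: change from neutral.** A constant offset drops out, and only proportional scaling of the response remains: d = s × standardised response.

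- Lowest: 0.05 × 0.2 = 0.01, which rejects in 5.0%.
- Highest: 0.10 × 0.8 = 0.08, which rejects in 6.8%.

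Most of the excess in Step 1 therefore comes from comparing values rather than changes.

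**Step 3: does scaling to height remove the artefact in values?** A simulation of 4,000 runs per case assumed men 8% larger, height CV 4%, the same shape in both sexes and exact proportionality to height.

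| CV of the distance | Unscaled t-test | Divided by height | Height as covariate |
|---|---|---|---|
| 20% | 46% | 4.6% | 4.9% |
| 30% | 23% | 4.7% | 5.4% |
| 40% | 16% | 5.1% | 5.0% |

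**Step 4: price of a height covariate.** With a sex-height correlation of 0.7 (assumed), the standard error of the sex effect is multiplied by √(1 / (1 − 0.7²)) = 1.40. In terms of detectable difference at 80% power, the unadjusted comparison gives (1.96 + 0.84) × √(2/50) = 0.56 SD. If the sexes differ in height by 1.5 to 2.0 SD (assumed), the variance is multiplied by 1.56 to 2.0, and the detectable difference becomes 0.56 × √1.56 = 0.70 to 0.56 × √2.0 = 0.79 residual SD.

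**Step 5: the fixed block.** With assumed foot lengths of 23.5–24 cm (women) and 26.5–27 cm (men), a lever of 70%–75% of foot length and tilt = arcsin(7 / lever), the 7 cm bar tilts the foot by 22.9–25.2 degrees in women and 20.2–22.2 degrees in men, about 13% more in women. If response were proportional to tilt (assumed), d would be 0.13 × 0.2 = 0.026 to 0.13 × 0.8 = 0.104, with rejection in 5.2% to 8.1%.

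**The case against.** The strongest reply is that the t-test wording can be read as comparing the differences between positions, that is, changes. On that reading the excess for FL and FC is near nominal (Step 2). This stands as far as it goes: the sentence is ambiguous, and the large figures belong only to the literal reading. It is a reason to settle the wording, since the two readings give very different error rates.

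A second reply is that the total sex difference, size included, is a legitimate target. The plan does not ask for a comparison at equal stature, and a true millimetre difference between men and women is a false positive only if size-free shape is meant. This also stands in part. The rationale for the male group is about heel-wearing habit, which gives some reason to separate size out, but not enough to make a height-adjusted estimate the main one.

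A reader might infer something stronger: that body size can produce a sex difference in response for all six parameters, because the same block tilts a shorter foot more. The documents do not support this. They do not say that spinal response follows foot angle, and they do not list foot length as collected. The illustrative effect in Step 5 is small. For FL and FC it also runs against the millimetre scaling: larger bodies raise the men's response while steeper tilt raises the women's, so +10% and +13% leave about 3%. The fixed 3 and 7 cm rises are, besides, the exposure that the protocol sets out to study.

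**Conclusion.** The point holds in a limited form. Followed literally, the planned male-female tests can report body size as a sex difference in FL and FC, and values at each position do not test a different response in any parameter. For FL and FC the rejection rate is about 8% to 51% under assumed size differences of 5%–10% and CVs of 25%–50%. On change from neutral it is about 5% to 7% if the standardised response is 0.2 to 0.8. Every size input is an assumption, so these figures show what can happen; they do not predict what this study will find.

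Two wider inferences should not be drawn. The primary comparison of neutral, 3 cm and 7 cm is not affected, because each participant serves as his or her own control. The millimetre-unit problem does not extend to the four angles. This is a low-severity improvement to a secondary analysis.

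**What to change.** In the Statistic analysis section:

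1. Make the male-female comparison on change from neutral (3 cm minus neutral, 7 cm minus neutral) for all six parameters.
2. For FL and FC, report that comparison also with each value divided by body height.
3. Describe a sex difference in FL or FC as postural only if scaling to height does not explain it; otherwise say that it is compatible with body size.
4. If a model with height as a covariate is shown, label it a sensitivity analysis. State that it targets the sex difference at equal stature, that its standard error is about 40% larger if the sex-height correlation is 0.7, and that height supplied by the participant is only a proxy for foot length.
5. Mention the unequal foot tilt from a fixed block as a limitation, with no analysis attached.

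Items 1 to 3 cost SAP wording and a few extra t-tests on data already collected. Item 4 is optional because it changes the question and loses precision.
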